6.1 Safety Run-in and Stopping Rules

Cohort A: ALR cohort

This is an open-label phase 2 study with a safety run-in period. The study can be considered for full enrollment only after the first 6 evaluable subjects have completed the safety run-in period which is defined as 28 days of cycle 1 of treatment, with 2 or less of the 6 evaluable subjects

experiencing potentially drug-related excess toxicities during safety run-in observation. The decision to proceed to full enrollment vs study discontinuation will be made in a Weill Cornell Medicine Data and Safety Monitoring Board (DSMB) Meeting in conjunction with the Investigators after careful consideration of all available safety and laboratory information.

Definition of potentially drug-related excess toxicity during safety run-in phase include:

Hematologic:

- Grade 4 neutropenia (ANC <500/mm³) lasting for >7 days
- Life-threatening Grade ≥ 3 neutropenia (ANC <1,000/mm³) with fever $\geq 38.3^{\circ}\text{C}$
- Grade 4 thrombocytopenia (<25,000/ mm³) that persists for ≥ 7 days
- Grade 3 thrombocytopenia associated with Grade ≥ 2 bleeding or requiring RBC or platelet transfusions

Non-Hematologic:

- Grade 3 tumor lysis syndrome if requiring dialysis
- Grade 3 rash that has not improved within 10 days to at least Grade 1 using a temporary drug hold of all study drugs and administration of up to 100 mg of prednisone PO or equivalent daily
- Grade ≥ 3 nausea, vomiting, or diarrhea uncontrolled by maximal supportive care and persisting greater than 7 days
- Treatment delay of any drug greater than 7 days for toxicity other than rash

In the safety run-in phase, if a subject ends treatment within the first cycle for reasons other than study drug(s) related toxicity (e.g. non-compliant, withdrawal of consent), they will be replaced. In addition, any subject that misses >7 days of acalabrutinib and/or lenalidomide for reasons other than rash will be replaced; subjects with AEs of rash that miss >10 days of acalabrutinib and/or lenalidomide will be replaced unless considered excessive toxicities. Any subject that requires rituximab discontinuation during the first cycle will be replaced.

Trial-wide stopping rule:

In the first 6 patients, if 2 or more experience potentially drug-related excess toxicities during the first cycle as defined in Section 6.1, the study team in conjunction with the DSMB will make a decision as to whether the treatment should be modified or the study halted.

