13. DATA AND SAFETY MONITORING PLAN (DSMP)

This is a multi-institution study. The data and safety monitoring for this study will be overseen by the Weill Cornell IRB as well as the principal investigators from each site. The study will be reviewed by the Weill Cornell Medicine Data and Safety Monitoring Board (DSMB) as an independent means of data and safety monitoring. Enrollment information, adverse event and safety information, protocol changes, and other interim data will be evaluated by the DSMB on an annual basis. After each evaluation, the Board will provide the principal investigator with recommendations for protocol modification, continuation, or termination.

An interim safety analysis will be performed after the first 6 evaluable subjects have completed the safety run-in period which is defined as 28 days of cycle 1 of treatment, to ensure no more than 2 out of the 6 evaluable subjects experiencing potentially drug-related excess toxicities during safety run-in observation (Section 6.1). The decision to proceed to full enrollment vs protocol modification vs study discontinuation will be made in a Weill Cornell Medicine Data and Safety

Monitoring Board (DSMB) Meeting in conjunction with the Investigators after careful consideration of all available safety and laboratory information.

After the first 16 patients, if the proportion of patients with drug-related grade 3 or higher non-hematologic AEs, as defined in Section 6.1, rise above 40% during the first cycle, the study team will temporarily suspend accrual to determine whether modification should be made to the protocol or the study should be halted due to unacceptable toxicity.

Subjects will be followed continuously throughout the study. Subjects may be removed from study treatment as specified in Section 6.6. The cumulative AEs and SAEs will be reviewed by the Sponsor-investigator on an ongoing basis to identify safety concerns. Investigators will discuss with the IRB whether subjects currently receiving therapy may continue as planned, or whether the protocol should be amended to change the study therapy.

We plan to expand the study to include a new cohort of 10 MCL patients who will receive treatment with the ALO regimen. The new cohort will contribute to the analysis of safety and feasibility secondary endpoints.

The ALO regimen will be considered feasible if all of the following conditions are met:

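### Cohort A safety run-in: the replacement rule can remove a subject who had a listed excess toxicity, so the 2-of-6 go rule may undercount; the options at exactly 2 of 6 also need stating once

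*Combined protocol and SAP*

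**What the plan says.** All of this concerns Cohort A, Section 6.1, unless another section is named.

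- **Go condition.** Full enrollment can be considered once 6 evaluable subjects have completed the 28 days of cycle 1, "with 2 or less of the 6 evaluable subjects" having an excess toxicity. Section 13 repeats the limit.
- **Stopping rule.** "In the first 6 patients, if 2 or more experience potentially drug-related excess toxicities during the first cycle", the study team and the DSMB "make a decision as to whether the treatment should be modified or the study halted".
- **Excess toxicity.** The list includes grade 4 neutropenia lasting more than 7 days and, separately, "Treatment delay of any drug greater than 7 days for toxicity other than rash".
- **Replacement.** "any subject that misses >7 days of acalabrutinib and/or lenalidomide for reasons other than rash will be replaced". The rash clause that follows (more than 10 days missed) ends differently: such subjects "will be replaced unless considered excessive toxicities". A subject who has to stop rituximab in cycle 1 is also replaced, with no exception.
- **Options.** Under the go rule in 6.1: "The decision to proceed to full enrollment vs study discontinuation will be made" by the DSMB with the investigators. Section 13 has three outcomes: "The decision to proceed to full enrollment vs protocol modification vs study discontinuation will be made".

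**The concern.** The run-in is the gate before the rest of Cohort A is treated: 28 planned less 6 in the run-in leaves 22. Its go rule counts toxicities among evaluable subjects, so the count depends on who stays evaluable. A toxicity serious enough to stop an oral drug for more than a week satisfies the wording of both the excess-toxicity list and the replacement rule. The text does not say which prevails, or whether a replaced subject's toxicity is still counted. If such subjects are replaced and left out, the go rule leans toward passing, and it does so through the subjects who tolerated treatment worst.

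The second issue is smaller. A count of exactly 2 satisfies the go condition and also triggers the stopping rule, and the three option lists differ on whether the trial may then continue unchanged.

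**Working it through.** The plan gives no operating characteristics for the run-in, so there is no stated figure to reproduce.

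**1. The clauses compared (6.1 and 6.8)**

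| Event in cycle 1 | Listed excess toxicity? | Replaced? | Exception for excess toxicity? |
|---|---|---|---|
| Oral drug missed >7 days, non-rash toxicity | yes | yes | none |
| Oral drug missed >10 days, rash | if it meets the grade 3 rash criterion | yes | yes |
| Rituximab discontinued | not in itself | yes | none |
| Treatment ended for a non-toxicity reason | no | yes | not needed |

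The last row (repeated in 6.8) suggests that toxic subjects were meant to stay. It covers ending treatment, not missed doses, so it does not settle the first row.

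**2. A concrete case: grade 4 neutropenia lasting more than 7 days**

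Inputs: lenalidomide is given on Days 1-21 and acalabrutinib continuously over 28 days; after Day 1, the scheduled cycle 1 CBCs fall on Days 8, 15 and 22 (5.2.2.2). Let d be the day of detection, when the hold starts. Grade 4 then persists at least through day d+7.

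- Table 6 (restart within the cycle allowed), minimum lenalidomide days missed = min(21, d+7) − d + 1.
  - d = 8: 15 − 8 + 1 = 8, which is more than 7. With weekly CBCs only, the count is still grade 4 on Day 15 and the next CBC is Day 22, so Days 8-21 are missed, which is 14.
  - d = 15: 21 − 15 + 1 = 7, which is not more than 7.
- Section 6.4.1 (both oral drugs off for the rest of the cycle), lenalidomide days missed = 21 − d + 1.
  - d = 8: 14.
  - d = 15: 7. Acalabrutinib is then missed for 28 − 15 + 1 = 14 days.
- Section 6.2 (acalabrutinib held only after more than 7 days at grade 4). With d = 15 confirmed at Day 22: 28 − 22 + 1 = 7.

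Detected at Day 8, this listed toxicity also meets the replacement clause under either dose rule. First found at Day 15, it does so only if 6.4.1 stops acalabrutinib for the rest of the cycle.

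**3. Effect on the go rule**

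Suppose 3 of the first 6 have an excess toxicity, one of them through a hold of more than 7 days. That subject is replaced by one without toxicity. Among evaluable subjects the count is 3 − 1 = 2 of 6 (go condition met) instead of 3 of 6 (not met). Among the first 6 patients it is still 3 of 6.

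For illustration only, let p be the true excess-toxicity rate and f the share of those toxicities that lead to replacement. Neither is in the documents. If replaced subjects are not counted, the rate among evaluable subjects is p(1 − f)/(1 − pf). The probability that the go rule fails (3 or more of 6) is then:

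| p | f = 0 | f = 0.25 | f = 0.50 |
|---|---|---|---|
| 0.2 | 0.099 | 0.054 | 0.021 |
| 0.3 | 0.256 | 0.159 | 0.072 |
| 0.4 | 0.456 | 0.320 | 0.169 |

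For p = 0.4 and f = 0.5 the rate is 0.20/0.80 = 0.25. The f = 0 column also applies if replaced subjects' toxicities are counted.

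**4. Exactly 2 of 6**

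P(X = 2) = 15 p²(1 − p)⁴ and P(X ≥ 2) = 1 − (1 − p)⁶ − 6p(1 − p)⁵.

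| p (assumed) | P(X = 2) | P(X ≥ 2) | Ratio |
|---|---|---|---|
| 0.2 | 0.246 | 0.345 | 0.71 |
| 0.3 | 0.324 | 0.580 | 0.56 |
| 0.4 | 0.311 | 0.767 | 0.41 |

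The ratio is the share of stopping-rule triggers at which the go condition is also met. These figures show how often the unclear count is reached, not how much harm follows.

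**The case against.** **The protocol never says that a replaced subject's toxicity is discarded, and the stopping rule is unaffected.** This stands. A reader might infer that three toxicities could pass unseen. The documents do not support that: the stopping rule counts the first 6 patients, and the DSMB decides on all available safety data. The 16-patient rule is a further check, although it covers only non-hematologic events and would miss the neutropenia case.

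**Delay and hold may be different events.** Section 6.4.3 uses delay for Day 1 of a cycle and interrupt for later days, so the listed delay and the missed-dose clause might not overlap. Within a 28-day cycle 1 window, however, a toxicity delay of an oral drug can hardly be anything but an in-cycle hold. The neutropenia case does not depend on this reading either, because prolonged grade 4 neutropenia is listed separately.

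**Replacing a subject who did not receive the full triplet is a legitimate choice.** It is, where the reason is not toxicity. Stopping rituximab is not itself an excess toxicity; the gap concerns a subject who stops it and also has one.

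**The two rules are compatible at 2 of 6.** Largely so. A reader might infer that they force opposite actions. They do not: the go rule is permissive, the stopping rule calls for a decision and not an automatic halt, and Section 13 lists proceeding. What remains is that the stopping rule names only modification or halting, and nothing says which list governs.

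**Onset is not detection.** A reader might also infer that any prolonged grade 4 neutropenia starting by Day 14 falls under both clauses. Onset on Days 9-14 would normally be found at the Day 15 CBC and costs only 7 lenalidomide days, so the firm example is limited to detection at Day 8.

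**Conclusion.** The concern holds in a limited form. As written, the Cohort A missed-dose clause orders replacement of subjects whose missed doses may themselves be an excess toxicity, and the exception that would prevent this is attached to rash alone. The go rule can therefore undercount, on the assumption that replaced subjects are not among the 6 evaluable. The documents do not fix the size. It is zero if those toxicities are counted, and the table in step 3 rests on assumed rates and shares. The undercount affects the go rule only.

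The overlap at exactly 2 of 6 is secondary. It can be read as a DSMB review zone, but one that would be reached 25% to 32% of the time at assumed true rates of 20% to 40%, so the permitted outcomes should be explicit. Neither issue touches the efficacy endpoint or its sample size.

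**What to change.** In Sections 6.1 and 13:

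- Extend the rash clause's exception to the missed-dose clause (more than 7 days) and the rituximab-discontinuation clause. State that any subject with an excess toxicity is evaluable, counted and not replaced.
- Use the same denominator in the go rule and the stopping rule.
- Give one option list, worded identically in both sections: 0-1 of 6, full enrollment may proceed; 2 of 6, mandatory DSMB review with proceed, modify or halt all available; 3 or more, no full enrollment without modification.
- Apply the same option list and counting rule to ALO. Section 6.1 repeats the overlap at 2 of 6 and the 7-day delay criterion there, but gives that cohort no run-in counting rule.

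Section 2.5 recommends starting ALO after ALR enrollment is complete, so the Cohort A run-in may already be over; the documents do not say. If it is, the report should state whether anyone was replaced and whether their toxicities were counted.

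The cost is a few sentences and no added patients. The run-in may flag slightly more often, and some counted subjects will have had an incomplete first cycle.

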6.2 Acalabrutinib

Dose modifications for the following treatment-emergent toxicities are provided in Table 4:

- Grade 4 neutropenia (< 500/µL) for > 7 days
- Grade 3 thrombocytopenia in presence of significant bleeding
- Grade 4 thrombocytopenia
- Grade 3 or 4 nausea, vomiting, or diarrhea, if persistent despite optimal antiemetic and/or anti-diarrheal therapy

- Any other Grade 4 toxicity or unmanageable Grade 3 toxicity

Table 4. Drug Modification Actions for Acalabrutinib

Occurrence	Action
1 st – 2 nd	Hold acalabrutinib until recovery to Grade \leq 1 or baseline; may restart at original dose level
3 rd	Hold acalabrutinib until recovery to Grade \leq 1 or baseline; restart at one dose level lower (100 mg QD)
4 th	Discontinue acalabrutinib

If acalabrutinib is reduced for apparent treatment-related toxicity, the dose need not be re-escalated, even if there is minimal or no toxicity with the reduced dose. However, if the subject tolerates a reduced dose of acalabrutinib for \geq 4 weeks then the dose may be increased to the next higher dose level, at the discretion of the investigator. Such re-escalation may be particularly warranted if further evaluation reveals that the AE that led to the dose reduction was not treatment-related. The maximum dose of acalabrutinib is 100 mg BID.

Treatment with acalabrutinib should be withheld for any unmanageable, potentially study drug-related toxicity that is Grade \geq 3 in severity. Acalabrutinib should be discontinued in the event of an acalabrutinib toxicity lasting more than 28 day. Any other clinically important events where dose delays may be considered appropriate must be discussed with the Principal Investigator.

6.3 Lenalidomide

6.3.1 Lenalidomide Dose Modification Steps

Lenalidomide dose will be reduced if patients experience toxicity as defined below in Section 6.3.2. Once the lenalidomide dose has been reduced, no dose re-escalation is permitted. If a new cycle is delayed for more than 4 weeks, remove the patient from protocol therapy. Patients who experience skin rash during cycle 1 which resolves to \leq grade 1 prior to cycle 2 day 1, can restart lenalidomide at the same dose level of cycle 1 without dose escalation.

Table 5. Lenalidomide Dose Levels

	Current Lenalidomide Dose	One Level Dose Reduction
Dose Level +1	20 mg / day	15 mg / day
Dose Level 0	15 mg / day	10 mg / day
Dose Level -1	10 mg / day	5 mg / day
Dose Level -2	5 mg / day	5 mg every other day
Dose Level -3	5 mg every other day*	See below

* Lenalidomide 5 mg every other day on Days 1-21 every 28 days is the minimum lenalidomide dose. Lenalidomide will be discontinued in patients who cannot tolerate this dose.

6.3.2 Instructions for Lenalidomide Dose Modifications or Interruption

Dose delay and dose reduction rules are as follows and in the table below.

- Lenalidomide dose reduction steps are outlined in Section 6.3.1.
- For treatment interruptions during a cycle, the 28-day schedule of each cycle will continue to be followed. Missed doses of lenalidomide are not made up.
- For treatment interruptions that delay the scheduled start of a new cycle, when toxicity has resolved as required to allow the start of a new cycle (Section 6.5), the restart day of therapy becomes Day 1 of the next cycle when all study medications will restart.

Table 6. Lenalidomide Dose Modifications	
NCI CTC Toxicity Grade	Dose Modification Instructions
Grade 3 neutropenia associated with fever (temperature $\geq 38.5^{\circ}$ C), Grade 4 neutropenia, or Grade 3 neutropenia > 7 days	
 Hold (interrupt) lenalidomide dose. Follow CBC weekly. If neutropenia has resolved to \leq grade 2 prior to Day 21 of the current cycle, restart lenalidomide at next lower dose level and continue through the scheduled Day 21 of the current cycle. Otherwise, omit for remainder of cycle and reduce the dose of lenalidomide by 1 dose level at the start of the next cycle. Omitted doses are not made up. If treatment is delayed for more than 4 weeks, discontinue all protocol therapy and notify the Principal Investigator.
Thrombocytopenia \geqGrade 3 (platelet count $< 50,000/\text{mm}^3$)	
 Hold (interrupt) lenalidomide dose. Follow CBC weekly. If thrombocytopenia resolves to \leq grade 2 prior to Day 21 of the current cycle, restart lenalidomide at next lower dose level and continue through the scheduled Day 21 of the current cycle. Otherwise, omit for remainder of cycle and reduce the dose of lenalidomide by 1 dose level at the start of the next cycle. Omitted doses are not made up.
Platelet count $< 50,000/\text{mm}^3$	
 Hold prophylactic anti-coagulation, if applicable. Restart prophylactic anti-coagulation when platelet count is $\geq 50,000/\text{mm}^3$.
Non-blistering rash Grade 3	
 If Grade 3, hold (interrupt) lenalidomide dose. Follow weekly. If the toxicity resolves to \leq grade 1 prior to Day 21 of the current cycle, restart lenalidomide at next lower dose level and continue through the scheduled Day 21 of the current cycle. Otherwise, omit for remainder of cycle and reduce the dose of lenalidomide by 1 dose level at the start of the next cycle. Omitted doses are not made up.
Desquamating (blistering) rash- any Grade	
 Discontinue lenalidomide. Remove patient from study.

Table 6. Lenalidomide Dose Modifications	
NCI CTC Toxicity Grade	Dose Modification Instructions
Neuropathy Grade 3	
 • If Grade 3, hold (interrupt) lenalidomide dose. Follow at least weekly. • If the toxicity resolves to \leq grade 1 prior to Day 21 of the current cycle, restart lenalidomide at next lower dose level and continue through the scheduled Day 21 of the current cycle. Otherwise, omit for remainder of cycle and reduce the dose of lenalidomide by 1 dose level at the start of the next cycle. Omitted doses are not made up.
	
 • If Grade 4, discontinue lenalidomide. Remove patient from study.
Venous thrombosis/embolism \geq Grade 3	
 • Hold (interrupt) lenalidomide and start therapeutic anticoagulation, if appropriate. • Restart lenalidomide at investigator's discretion (maintain dose level). • See Anticoagulation Consideration (Section 8.1.1)
Tumor lysis syndrome \geq Grade 3	
 • Interrupt therapy. • May resume study drug when the TLS resolves to \leq Grade 1 (decrease one dose level)
Tumor Flare \leq Grade 2	
 • at the investigators discretion, may initiate therapy with corticosteroid, NSAIDs and/or Narcotics • Continue Study drug
Tumor Flare Grade 3 or 4	
 • Hold (interrupt) dose and start corticosteroids, NSAIDs and/or Narcotics. • When toxicity resolves to \leq grade 1 restart at next lower dose level
other non-hematologic toxicity \geq Grade 3	
 • Hold (interrupt) lenalidomide dose. Follow at least weekly. • If the toxicity resolves to \leq grade 2 prior to Day 21 of the current cycle, restart lenalidomide and continue through the scheduled Day 21 of the current cycle. Otherwise, omit for remainder of cycle. Omitted doses are not made up. For toxicity attributed to lenalidomide, reduce the lenalidomide dose by 1 dose level when restarting lenalidomide.

6.4 Dose Modification for Potential Overlapping Toxicities

Table 7: Dose Modification Schedule for Potential Overlapping Toxicities

	Lenalidomide Dose	Acalabrutinib Dose
Dose Level +1	20 mg / day	100 mg BID
Dose Level 0	15 mg / day	100 mg BID
Dose Level -1	10 mg / day	100 mg BID
Dose Level -2	10 mg / day	100 mg QD
Dose Level -3	5 mg / day	100 mg QD

6.4.1 Neutropenia

For grade 3 or 4 neutrophil count decreased on day 1 of a cycle, delay lenalidomide and acalabrutinib until ANC improves to \leq grade 2, then resume lenalidomide and acalabrutinib with one dose level reduction (Table 7) for all subsequent cycles.

For grade 3 or 4 neutrophil count decreased during a cycle, interrupt lenalidomide and acalabrutinib for the remainder of the cycle. Resume lenalidomide and acalabrutinib (if ANC \leq grade 2) at the next cycle with one dose level reduction (Table 7) for all subsequent cycles.

For febrile neutropenia at any time during a cycle, interrupt or delay lenalidomide and acalabrutinib until toxicity improves to \leq grade 2, then resume lenalidomide and acalabrutinib with one dose level reduction (Table 7) for all subsequent cycles.

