3.2 Inclusion Criteria

- Histologically confirmed diagnosis of mantle cell lymphoma
- Age \geq 18 years
- No prior systemic therapy for lymphoma
- Measurable disease defined by a tumor mass \geq 1.5 cm in one dimension and measurable in two dimensions; patients with measurable spleen disease are allowed
- Treatment should be indicated according to the treating physician
- ECOG performance status \leq 2
- Required initial laboratory parameters:
 - Absolute neutrophil count (ANC) \geq 1000 cells/mm³
 - Platelet count \geq 75,000 cells/mm³
 - Calculated creatinine clearance \geq 30 ml/min by Cockcroft-Gault formula
 - Total bilirubin \leq 1.5 x ULN
 - AST/SGOT and ALT/SGPT \leq 3.0 x ULN
- Able to take aspirin (81 or 325 mg) daily as prophylactic anticoagulation (patients intolerant to ASA may use low molecular weight heparin).
- All subjects must be registered into the mandatory Revlimid REMS® program, and be willing and able to comply with the requirements of Revlimid REMS®.
- Patients of reproductive potential agree to use highly effective birth control throughout their participation in this study, for at least 28 days following study termination, and for 160 days for males and 12 months for females after the last dose of rituximab, 180 days for males and 18 months for females after the last dose of obinutuzumab.
- Females of reproductive potential must adhere to the scheduled pregnancy testing as required in the Revlimid REMS® program. Females of childbearing potential (FCBP) must have a negative serum or urine pregnancy test with a sensitivity of at least 50 mIU/mL within 10 – 14 days and again within 24 hours prior to prescribing lenalidomide for Cycle 1 (prescriptions must be filled within 7 days). FCBP must either commit to continued abstinence from heterosexual intercourse or begin one highly effective method and one additional effective method AT THE SAME TIME, at least 28 days before and continue for at least 28 days after the last dose of lenalidomide (or 2 days after the last dose of acalabrutinib, whichever is longer). FCBP must also agree to ongoing pregnancy testing. Men must agree to use a latex condom during sexual activity with a FCBP through one week post last dose even if they have had a successful vasectomy. Men must also agree to refrain from sperm donation during the same timeframe. See Appendix I: Risks of Fetal Exposure, Pregnancy Testing Guidelines and Highly Effective Birth Control Methods.

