5.1.1 Induction

Cohort A: ALR cohort

- Cycles 1-12, 1 cycle = 28 days
- Acalabrutinib 100 mg BID continuous
- Lenalidomide on days 1-21 (15 mg for cycle 1, then escalate as tolerated to 20 mg)
- Rituximab 375 mg/m² on days 1, 8, 15, 21 of cycle 1 then day 1 of cycle 4, 6, 8, 10, 12

Cohort B: ALO feasibility cohort

- Cycles 1-12, 1 cycle = 28 days
- Acalabrutinib 100 mg BID continuous
- Lenalidomide on days 1-21 (15 mg for cycle 1, then escalate as tolerated to 20 mg)
- Obinutuzumab on days 1, 8, 15 of cycle 1, day 1 of cycles 2-6, then every 2 cycles

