5.3.2 Lenalidomide Administration

The lenalidomide starting dose will be based on baseline calculated creatinine clearance as follows:

Table 3. Lenalidomide Starting Dose Based on Renal Function at Study Entry

Baseline Calculated Creatinine Clearance (by Cockcroft-Gault)	Starting Lenalidomide Dose
≥ 60 ml/min	15 mg daily on Days 1 - 21 of each 28-day cycle
≥ 30 and < 60 ml/min	5 mg daily on Days 1 - 21 of each 28-day cycle

For patients with normal renal function (creatinine clearance \geq 60 ml/min), the starting dose will be lenalidomide 15 mg daily with escalation to 20 mg if no excess toxicity. For patients with creatinine clearance \geq 30 and $<$ 60 ml/min, the starting dose will be lenalidomide 5 mg daily with escalation to 10 mg if no excess toxicity. The lenalidomide dose may only be increased if the prior treatment cycle was completed without requiring dose modifications, interruptions or delays due to toxicity. Excess toxicity will be defined as grade 3 or 4 non-hematologic toxicity or grade 4 hematologic toxicity (see Section 6.1).

Prophylactic aspirin or low molecular weight heparin are to be given to patients with a high risk of developing DVT/PE or arterial thromboses unless contraindicated. High risk is defined as a history of DVT/PE, a known hypercoagulable state, and/or taking a concomitant medication associated with an increased risk for a thromboembolic event. Patients with diabetes mellitus or coronary artery disease are considered to be at high risk for arterial thromboembolic events.

Prescriptions for lenalidomide must be filled within 7 days. Dosing will be in the morning at approximately the same time each day. Lenalidomide capsules should be swallowed whole, and should not be broken, chewed, or opened. If a dose of lenalidomide is missed, it should be taken as soon as possible on the same day. If it is missed for the entire day, it should not be made up. Patients who take more than the prescribed dose of lenalidomide should be instructed to seek emergency medical care if needed and contact study staff immediately.

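### Table 7, which Section 6.4 requires for dose reductions, has no row for the renal starting combination (lenalidomide 5 mg daily with acalabrutinib 100 mg BID), and it conflicts with Tables 5 and 6 without saying which prevails

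*Combined protocol and SAP*

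**What the plan says.** Section 3.2 admits patients whose creatinine clearance is at least "30 ml/min by Cockcroft-Gault formula". Section 5.3.2 (Table 3) sets a separate lenalidomide start for those at 30 to <60 ml/min: "the starting dose will be lenalidomide 5 mg daily with escalation to 10 mg if no excess toxicity". Section 5.1.1 gives one acalabrutinib dose in both cohorts, "Acalabrutinib 100 mg BID continuous", with no renal variant. The renal group therefore starts on lenalidomide 5 mg daily with acalabrutinib 100 mg BID.

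Sections 6.4.1 to 6.4.3 cover grade 3-4 or febrile neutropenia, grade 3-4 thrombocytopenia and grade 3 maculopapular rash. Each orders a one-level reduction of both drugs by reference to Table 7, for example "then resume lenalidomide and acalabrutinib with one dose level reduction (Table 7) for all subsequent cycles" in 6.4.1. The table is titled "Table 7: Dose Modification Schedule for Potential Overlapping Toxicities". Its lowest row that keeps acalabrutinib BID is "Dose Level -1 10 mg / day 100 mg BID". Its only row with lenalidomide 5 mg, which is also its last, is "Dose Level -3 5 mg / day 100 mg QD".

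Section 6.3 has a separate lenalidomide ladder (Table 5), with event-specific rules in Table 6 that also cover neutropenia, thrombocytopenia and grade 3 rash. That ladder goes lower than Table 7: "Lenalidomide 5 mg every other day on Days 1-21 every 28 days is the minimum lenalidomide dose". Lenalidomide is discontinued in patients who cannot tolerate that dose.

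**The concern.** A dose-reduction rule should return one answer for every dose state the protocol itself creates. Here a starting regimen prescribed in Section 5.3.2 lies outside the table that governs its reduction, and a second set of rules for overlapping events gives another answer.

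The protocol treats this group differently at the outset, and Section 7.2.3 reports that about two-thirds of lenalidomide leaves the body unchanged in urine. What is at stake is mainly consistent handling of toxicity across sites.

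There is also a link to the endpoints. Safety and tolerability of ALR is a secondary objective (Section 1.2). ALO feasibility requires that no more than 2 of 10 patients stop for adverse events in the first year (Sections 6.1 and 11.1). If one site reads the rule as leaving no step and stops treatment while another reduces and continues, the same toxicity is counted differently against that limit.

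**Working it through.** The plan states no figure to reproduce. The check is a lookup in the two ladders, followed by cycle totals.

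**1. Table 7 lookup** (lenalidomide per day / acalabrutinib 100 mg BID or QD):

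| Current doses | Table 7 level | One level down |
|---|---|---|
| 20 mg / BID | +1 | 15 mg / BID |
| 15 mg / BID | 0 | 10 mg / BID |
| 10 mg / BID | -1 | 10 mg / QD |
| 10 mg / QD | -2 | 5 mg / QD |
| **5 mg / BID (renal start)** | **no row** | **undefined** |
| 5 mg / QD | -3 | no lower row, no instruction |

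Sections 6.4 to 6.4.3 give no instruction for a patient who matches no row.

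**2. Table 5 against Table 7.** The same level number means different lenalidomide doses:

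| Level | Table 5 | Table 7 |
|---|---|---|
| -2 | 5 mg daily | 10 mg daily (acalabrutinib QD) |
| -3 | 5 mg every other day | 5 mg daily (acalabrutinib QD) |

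**3. Results for a patient on 5 mg / BID after a triggering event:**

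- *Move to the Table 7 row that contains 5 mg (level -3).* Lenalidomide is unchanged and acalabrutinib goes to QD. Lenalidomide per cycle: 21 doses × 5 mg = 105 mg.
- *Follow Tables 5 and 6.* Lenalidomide goes to 5 mg every other day. Dosing on days 1, 3, …, 21 gives 11 doses × 5 mg = 55 mg. These tables do not address acalabrutinib, which has its own rules in Section 6.2.
- *Conclude that 5 mg is already the lowest Table 7 lenalidomide dose and no step is left.* The table gives no next action.

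Ratio of the first two: 105 / 55 = 1.9, about twofold.

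**4. Results for a patient on 10 mg / BID**, including a renal patient who has escalated. This pair is in Table 7 (level -1), so there is no missing row, but the two ladders disagree:

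- Table 5 goes to 5 mg daily: 21 × 5 = 105 mg per cycle.
- Table 7 keeps 10 mg daily, 21 × 10 = 210 mg per cycle, and lowers acalabrutinib to QD.

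Ratio: 210 / 105 = 2.

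**5. Which section governs.** Table 6 and Section 6.4 overlap on neutropenia, thrombocytopenia and grade 3 rash. They also differ on timing. For neutropenia or thrombocytopenia arising within a cycle, Table 6 allows lenalidomide to restart in that cycle if counts recover before day 21, while 6.4.1 and 6.4.2 hold both drugs until the next cycle (6.4.1 treats febrile neutropenia separately). No text ranks the two sections.

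**6. Who meets the missing row.** Renal-start patients meet it until they escalate to 10 mg, and throughout if they never do. A patient with normal renal function could also reach 5 mg / BID through lenalidomide-only steps under Tables 5 and 6.

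**The case against.** The strongest case against is that the protocol is workable. Within Table 7, level -3 is the only row that exceeds the renal starting pair on neither drug, so a sensible site would go there. Holding lenalidomide while lowering acalabrutinib is Table 7's own pattern from level -1 to -2. Tables 5 and 6 also supply a lenalidomide step below 5 mg daily, so these patients are not without a rule, and the reading that nothing is left is weak.

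This stands in part. Level -3 is a reasonable inference, but no text makes it the one-level reduction from a pair that is not a level. The lenalidomide-only step is a second answer from a section that 6.4 does not cite for its reductions, and it leads to a dose absent from Table 7. Two plausible answers with no order of precedence are the problem.

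A reader might infer something stronger: that a site could call the renal start level 0, step to level -1 and so double lenalidomide to 10 mg, giving a fourfold spread. The documents do not support that. Section 6.4 orders a reduction, Table 7 fixes level 0 at 15 mg, and Section 5.3.2 allows an increase only after a cycle free of modification, interruption or delay for toxicity.

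**Conclusion.** The gap is real and should be corrected. A protocol-specified starting combination has no defined one-level reduction in the table Section 6.4 requires. That table is silent below level -3, and it conflicts with Tables 5 and 6 without a stated precedence. From a 5 mg start the competing lenalidomide results differ about twofold (105 versus 55 mg per cycle, counting every-other-day dosing from day 1). From 10 mg / BID they also differ twofold, but there the fault is disagreement between tables, since the row exists.

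Two further inferences should not be drawn.

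- **A patient count.** One could assume that 10-30% of the 38 patients have reduced clearance and apply the cited grade 3-4 neutropenia rates of 38-50%, giving 0.10 × 38 × 0.38 = 1.4 to 0.30 × 38 × 0.50 = 5.7 patients. The renal share is not in the documents. The rates come from other regimens (Sections 2.2.1 and 2.2.4) and are not reported for patients starting at 5 mg. Only patients still on 5 mg / BID at the event meet the missing row. The number affected cannot be derived.
- **Loss of interpretability.** Section 11.3 plans no renal-subgroup or dose-intensity analysis, so the documents do not support saying that such results become uninterpretable.

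The finding rests on the table text alone and holds if even one patient with clearance 30 to <60 ml/min is enrolled.

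**What to change.** Reconcile Sections 5.1.1, 5.3.2 (Table 3), 6.3.1 (Table 5), 6.3.2 (Table 6) and 6.4 to 6.4.3 (Table 7) so that:

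- every protocol-specified starting combination, including the renal one, has a defined place in the Section 6.4 reduction schedule;
- a given level number means the same lenalidomide dose in Tables 5 and 7;
- the text says whether Section 6.3.2 or Section 6.4 governs toxicities that fall under both, and whether the every-other-day step in Table 5 is available under 6.4;
- the text says what follows the lowest Table 7 level.

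The sponsor's clinicians choose the doses; none is proposed here. The cost is amended table wording and a memo to sites, with no new procedures or patients.
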